Metabolic Mapping and Cardiac Resynchronization (Aim 1)

NCT# 03420833

June 20, 2021

STUDY OVERVIEW

Title	Metabolic Mapping and Cardiac Resynchronization (Aim 1)						
Running Title	Metabolic Mapping and CRT						
IRB Protocol Number	17-003359						
Phase	Pilot						
Principal	[name]						
investigator	Mayo Clinic						
Objective	To determine early alterations in metabolic pathways and metabolomics biomarkers in patients with mild heart failure (HF) and left bundle branch block (LBBB), and their role in the prediction of outcomes by early CRT.						
Study Design	Single-center, randomized cross-over study						
Overall Study Design	We plan to complete subject enrollment by the end of Year 3. Data validation, adjudication and analysis will be finished by the end of Year 5.						
Subject Participation Duration	Approximately 12 months						
Primary	Primary efficacy objectives (composite endpoint)						
Objectives	The study primary endpoint is a reduction in the LV end-systolic volume index (LVESVI, reverse LV remodeling) in the CRT-ON gorup as compared to the CRT-OFF group.						
	 Primary Safety Objective Freedom from system-related complications in randomized subjects will be calculated at 1, 6, and 12 months post implant to determine the safety profile, including the device pocket hematoma, pneumothorax, myocardial performation, lead dislodgement, lead revision, and device-related infection This safety profile will be balanced against efficacy to quantify the risk-benefit ratio. 						
Secondary	Secondary efficacy objectives						
Objectives	 Hospital admission for HF Increase in NT pro-BNP level by 30% 						
	 Increase in NT pro-вые level by 30% Sustained ventricular tachycardia or fibrillation greater than 30 seconds 						
	 Decrease in LVEF to ≤34% 						
	Death						
Device	BIOTRONIK Edora HF-T QP, or Ilivia HF-T QP DF4						
Number of Subjects	100 subjects (of these 30 will be female)						
Subject Inclusion	• LVEF 35%-50%						
Criteria	 NYHA class I-II QRS duration of ≥120ms 						
	Left bundle branch block (LBBB)						
	Patient is able to receive a transvenous pectoral CRT implant						

	 Patient is able to sign informed consent Two echocardiograms are required to confirm LVEF≤ 50% (one echo must be within 12 months of enrollment) Patient is on optimal and stable medical therapy (ACE inhibitor or AT1 blocker, beta blocker, etc. over the last 6 months)

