We propose a single-center, randomized cross-over study design. The study will be approved by the Mayo Clinic Institutional Review Board, and a consent form will be signed by each participant. We will enroll 100 patients at Mayo Clinic, Rochester, Minnesota, who have LVEF of 35% to 50%. Of these patients, 30 will be women. Participants will undergo placement of a CRT-pacemaker (CRT-P) after the completion of the baseline assessment if all inclusion and none of the exclusion criteria are met. Participants who have an ICD in place, or who meet clinical indication for an ICD, will undergo placement of a CRT-defibrillator (CRT-D). Defibrillation will not be added for patients who do not have an existing ICD system or do not meet clinical indications for an ICD. Participants who have a successful CRT implantation will be randomly assigned 1:1 to have the CRT programmed on (CRT-ON, treatment group) or off (CRT-OFF, control group) within 7 days of completing the implant procedure. Participants will be randomly assigned using an allocation method defined by a biostatistician. Investigators managing HF in study participants will be blinded to the randomization method to minimize potential bias. A washout period after the device implantation will not be used in this study.¹⁹ At 6-month follow-up, the CRT function will be turned on in the CRT-OFF group and the CRT function will be turned off in the CRT-ON group in a cross-over design. All participants will cross-over at the 6-month follow-up visit. At 12-month follow-up, when each patient completes his/her cross-over 6-month therapy, the CRT function will be programmed on to provide chronic benefit from CRT for a battery life of 8.6 years. The subjects will be blinded from whether biventricular pacing is on or off. For participants who receive a CRT-D, the defibrillation function will be programmed on for the duration of the study.

Study device

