Peripheral venous blood samples will be collected before CRT, at 6-month and 12-month follow-up (either CRT-ON for 6-month or CRT-OFF for 6-month). At implant, blood samples from femoral artery and coronary sinus will be collected to measure transcardiac metabolomic gradient. More often, the LV lead deliver sheath for coronary sinus cannulation is able to be advanced into the beginning of lateral vein to facilitate the LV lead placement (70%-80%), where blood sample will be collected to determine the regional metabolic profile as shown in **Figure 12**. The rational for collecting the regional blood is to determine 1) whether there is a differential metabolisms between ICM (discrete scar vs no scar accessed by echocardiography) vs NICM (diffused fibrosis), and 2) metabolic feature at the most delayed conduction area at the LV lateral wall in coping with QRS-LV time.

Muscular samples collection for metabolomics measurement

When the patient is undergoing a CRT device implant, a pre-pectoral pocket is made routinely to house the generator. The skin and subcutaneous planes are dissected to expose the fascia of the pectoralis major. A small piece (0.5-1.0g) of the chest muscle (Pectoralis major) biopsy will be taken for metabolomics analysis, and mitochondrial physiology. Approximately 100mg of muscle tissue will be immediately used to evaluate mitochondrial capacity and bioenergetic efficiency using high-resolution respirometry and spectrofluorometry, as we have described previously [sup 1,2]. The remainder of the muscle tissue will be immediately blotted, frozen in liquid nitrogen, and stored at -80 C. Muscle mitochondrial content will be evaluated by laboratory-based enzymatic assays, protein expression, and mRNA abundance [sup 3]. Mass spectrometry and NMR spectroscopy will be used to detect and quantitate metabolites in muscle tissue lysates [sup 4]. Muscle biopsy may cause bleeding. We will use readily available cautery to stop the bleeding.

Device programming and follow-up

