b. Amino acids are important substrates for energy production in the heart. Through a series of reactions, branched-chain amino acids (BCAAs) can be converted to metabolic intermediates and fed into the tricarboxylic acid (TCA) cycle as potential sources of anaplerotic input (Figure 14, red box). Due to the down regulation of gene expression related to the BCAA degradation and utilization, specifically, valine, leucine and isoleucine are accumulated in HF.^{53,81,82} Our preliminary data (shown in Figure 6 and 10), showed that the level of these BCAAs were disturbed even in mild HF and was significantly lower in CRT non-responders than in CRT responders with severe HF. Further, amino acids are not only cell building blocks, energy source and signaling molecules but are also regulators of gene expression and protein synthesis. Taken together, the BCAAs are critical metabolite markers in HF.

c. Using the new technology of whole blood ¹⁸O metabolic labeling, we will test the hypothesis that the 2,3-BPG[¹⁸O] and G-3-P[¹⁸O] turnover rates are reduced, while inorganic phosphate (Pi[¹⁸O]) and γ -ATP[¹⁸O] are elevated in mild LV dysfunction in which the impaired O2 and substrate transport and ATP synthesis may precede the HF symptoms (Figure 13).

d. We will develop strong metabolic biomarkers as proposed in above to determine the prognostication with clinical outcomes in patients with mild HF.

Primary clinical efficacy objective

The study primary endpoint is a reduction in the LV end-systolic volume index (LVESVI, reverse LV remodeling) in the CRT-ON group as compared to CRT-OFF group.

Secondary clinical efficacy objectives (composite events)

 Hospital admission for HF; 2) Increase in NT pro-BNP level by 30% and its predictive value of response to CRT; 3) Sustained ventricular tachycardia or fibrillation greater than 30 seconds; 4) Decrease in LVEF to ≤35%; and 5) death.

The analytical imprecision of natriuretic peptides depends on the assay but for NTprpoBNP it is roughly 1.6%. Inter and intradividual variation is roughly 30% (American Journal of Cardiology. 92(5):628-31, 2003). Thus values above 30% have been suggested to define significant changes in natriuretic peptides (Journal of Investigative Medicine. 61(6):950-5, 2013 Aug,). This value was shown to have prognostic significance in the VALHEFT trial (Journal of the American College of Cardiology. 52(12):997-1003, 2008 Sep 16) and thus will provide an end point in our proposed analysis.

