Primary safety objectives

Freedom from system-related complications in randomized participants will be calculated at 1, 6, and 12 months post-implant to determine the safety profile, including the device pocket hematoma, pneumothorax, myocardial perforation, lead dislodgment, lead revision, and device-related infection. This safety profile will be balanced against efficacy to quantify the risk-benefit ratio. This analysis will occur when all subjects have completed study procedures.

Sample Size Considerations and Statistical analysis

The timing of primary endpoint analysis will occur when all subjects have completed study procedures. The primary endpoint for Aim 1 is the change in LVESVI. We propose a paired t-test, which combines both

randomized groups together (n=50 + 50 = 100), and compares the CRT-ON condition to the CRT-OFF condition. The power can be estimated based on REVERSE (LVEF \leq 40%) showing a mean change of -18.4 +/- 29.5 ml/m2. Let us assume that in the current mildly impaired EF group, the reduction will be, not -18, but -12. Assuming the SD is 26, the power for the one-sample paired t-test is over 99%. If we assume an 80% attrition (n=40 + 40), the detectable difference with 80% power is 8.3 ml/m2, less than half of that observed in REVERSE. A secondary analysis will be a generalized linear model in which baseline, period 1, and period 2 values of LVESVI will be analyzed together, with the possibility of an order effect. If no order effect is detected, then the analysis will amount to the paired t-test already described. Data may be missing due to the occurrence of interim events. This would mean that the data are not missing at random. We propose to accommodate this by a rank-based procedure, in which the ON-OFF differences are ranked in both groups together. As a secondary endpoint, we will analyze the composite clinical endpoint described above. This endpoint will be analyzed as the time to the first of any of these component events. The crossover design can be accommodated by fitting the treatment variable ON-OFF as a time dependent binary variable that is 1 (ON) or 0 (OFF). Order effects can be accommodated by including interactions with time-period in the model.

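### The 30% NT-proBNP rise that counts as a composite event equals the variation the protocol quotes; if that figure is a within-person CV, chance could be the largest single source of composite events

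*Combined protocol and SAP*

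**What the plan says.** The Study Overview lists "Increase in NT pro-BNP level by 30"% among the secondary objectives. The section on secondary clinical efficacy objectives (composite events) repeats it as item 2, "Increase in NT pro-BNP level by 30% and its predictive value of response to CRT", beside HF admission, sustained VT/VF, LVEF decrease and death.

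The same section gives the reasoning for the cut-off. On analytical imprecision: "for NTprpoBNP it is roughly 1.6"%. On biological variation: "Inter and intradividual variation is roughly 30"%. It then concludes: "Thus values above 30% have been suggested to define significant changes in natriuretic peptides". It adds that this value was prognostic in another trial.

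Under Sample Size Considerations and Statistical analysis the composite is handled as follows: "This endpoint will be analyzed as the time to the first of any of these component events". Treatment enters as a time-dependent ON/OFF variable.

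The section on blood sample collection sets the sampling times: "Peripheral venous blood samples will be collected before CRT, at 6-month and 12-month follow-up". The Schedule of Events marks biomarker blood at screening, implant, 6 months and 12 months. The documents do not say which sample is the reference for the rise, whether a rise must be confirmed, or whether the 30% describes one sample or a serial change. They give no expected event rate for the composite.

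**The concern.** A threshold for change should be judged against the variability of a change. A change is the difference between two measurements, each with its own error, so its SD is √2 times that of one measurement. The protocol moves directly from a variation figure to a change threshold of the same size.

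Three things follow if the 30% is a single-sample within-person CV:

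- **Dilution.** Chance crossings occur equally with CRT on and off, and pull the ON/OFF hazard ratio towards 1.
- **Lost follow-up.** In a time-to-first-event analysis, a patient with a chance rise at 6 months leaves the risk set at the moment of crossover. Any later admission, arrhythmia or death in period 2 does not count.
- **Carry-through.** The metabolomics data analysis section relates the principal components to the clinical endpoint by Cox regression, so noise events would also weaken that analysis.

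**Working it through.** The documents give no figure for the composite to reproduce: no event rate, event count or power. The check is therefore how often a stable patient would cross the threshold.

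**Inputs from the documents**
- Threshold: ratio 1.30.
- Variation: 30%, read here as a within-person CV (an assumption; see the sensitivity table).
- Assay imprecision: 1.6%.
- Visits: 6 and 12 months.
- Sample size: "We will enroll 100 patients at Mayo Clinic".
- Comparator rates: LVEF fall 17% at 1 year (100% − 83% event-free, LBBB group, cut <35%, Preliminary results); HF admission 5.7-7.2% and cardiovascular death 4.0-6.0% per year (Background and Significance, from another trial's population). No VT/VF rate is given.

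**One visit, no true change**
- Total CV = √(0.30² + 0.016²) = 0.3004. The assay part is negligible.
- Linear scale: SD of a change = √2 × 0.3004 = 0.425. A 30% rise is 0.30/0.425 = 0.71 SD, and P = 24%.
- Log-normal scale: σ = √ln(1 + 0.3004²); SD of the log ratio = √2 × σ = 0.416. ln 1.3 = 0.262, so z = 0.262/0.416 = 0.63, and P = 26%.

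**Either visit against one shared baseline**
- The two changes share the baseline error, so their correlation is 0.5. From the bivariate normal, P = 37% (linear) or 40% (log-normal), or about 40 of 100 patients.
- About 26 of these first cross at 6 months and about 40 − 26 = 14 at 12 months.
- If each visit were instead compared with the preceding sample (correlation −0.5), P = 51% on the log-normal scale. The unnamed reference sample therefore matters.

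**Sensitivity to the meaning of 30%** (log-normal, shared baseline)

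| Reading | One visit | 6 or 12 months |
|---|---|---|
| CV 30% | 26% | 40% |
| CV 25% | 23% | 35% |
| CV 20% | 18% | 28% |
| CV 15% | 11% | 18% |
| CV 10% | 3% | 6% |
| 30% is already a 95% serial-change limit (CV about 11-13%) | 2.5-5% | 5-9% |

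The two-visit figure passes the 17% LVEF rate at a CV of about 14.6%.

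**Share of first events.** A simulation of 1,000,000 patients used CV 30%, the comparator rates above and an assumed VT/VF rate of 0-5%. Chance NT-proBNP rises come first, excluding ties, in 53-60% of composite events; LVEF fall comes first or ties in 22-25%. Composite incidence goes from 25-31% without the component to 55-59% with it.

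**Dilution, as an illustration.** Assume 14% genuine events per OFF period and a true hazard ratio of 0.60. Cumulative hazards are −ln 0.86 = 0.151 (OFF) and 0.60 × 0.151 = 0.090 (ON). Chance crossings of 26% add −ln 0.74 = 0.301 to both. The observed ratio becomes (0.090 + 0.301)/(0.151 + 0.301) = 0.87.

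**Reference change value for a rise.** One-sided 95% at CV 30%: linear 1.645 × √2 × 0.30 = +70%; log-normal exp(1.645 × 0.416) − 1 = +98%. The two-sided limits (+83% and +126%) do not suit an event defined only as a rise. On the log-normal model a cut at +83% would still be crossed by chance in about 7% at one visit.

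**The case against.** The strongest objection is that the ranking depends on what the 30% is. The protocol merges inter- and intra-individual variation into one figure and labels it neither as a single-sample CV nor as a change limit. Its next sentence presents 30% as a limit for change. If it is already a serial-change limit, chance gives roughly 5-9% by 12 months and LVEF fall is the larger component. This stands. Placing the figure beside the assay imprecision favours reading it as a CV, but does not prove it.

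Other points also limit the claim:

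- **True change.** The calculation assumes stable patients. If CRT lowers NT-proBNP, fewer cross. With assumed log shifts of −0.1, −0.2 and −0.3 at both visits (CV 30%, upper background rates), the chance share of first events is 45%, 37% and 28%; at −0.3 it is below the LVEF share of 34%.
- **Comparators.** The rates come from other populations, and VT/VF has none. The LVEF component is ≤34% in the overview and ≤35% in the main text, with entry allowed from 35%, so its rate could exceed 17%.
- **Pre-emption.** Rises first seen at 12 months pre-empt nothing in the randomised periods, and an LVEF fall found at the same 6-month visit ties with a chance rise. Only the 6-month crossings can mask later events.
- **Prognosis.** The protocol cites prognostic value for this cut-off. That may hold for groups, but it does not make one unconfirmed crossing a reliable event in an individual.
- **Weight.** This is a secondary endpoint in a pilot, with no power claim attached.

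A reader might infer that chance is bound to supply most composite events, or that the composite would mainly report assay noise. The documents support neither: the first depends on the CV reading and the assumptions above, and the assay contributes only about 1.6%.

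**Conclusion.** The threshold equals the quoted variation, and the protocol makes no allowance for comparing two samples. That much rests on its own text. If 30% is a within-person CV, about 26% of stable patients cross at one visit and about 40% by 12 months, and chance could be the largest single source of composite events. Against the 17% LVEF figure that ranking holds down to a CV of about 14.6% and reverses below it. It assumes no true change, log-normal errors and one shared baseline. About 26 of 100 patients would end time-to-first-event follow-up at 6 months, before period 2. The recommended change does not depend on the ranking and should be made. The primary LVESVI analysis is unaffected.

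**What to change.** 1. Analyse NT-proBNP as its own secondary endpoint: the within-patient log ratio of the CRT-ON value to the CRT-OFF value. This suits the crossover and needs no threshold.
2. Make the composite without the NT-proBNP rise the main version, and report the composite with it as supportive.
3. State whether the quoted 30% is a within-person CV, a between-person figure or a serial-change limit.
4. If a binary rule is kept, name the reference sample and set the cut-off from a one-sided reference change value for the stated within-person CV (about +98% log-normal or +70% linear at CV 30%).

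The cost is protocol and SAP wording only, since the samples are already scheduled at baseline, 6 and 12 months. The downside is fewer composite events: in the simulation at CV 30%, 25-31% of patients instead of 55-59%.

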All adverse events occurring related to the procedure or protocol required testing during the study, including those not meeting the criteria of an Unanticipated Adverse Device Effect (UADE) will be recorded on the appropriate case report form. Records of these events will be maintained and reports submitted to the FDA and IRB according to the regulatory requirements. Expected clinical adverse events and nonsignificant (not serious) clinical adverse events will not be reported. Expected clinical adverse events and anticipated adverse device effects are those listed below.

The safety and clinical performance of market-released CRT systems have been demonstrated through previous clinical studies. All products used within this study are FDA approved and market-released. Therefore, it is not anticipated that subjects enrolled in this study will be exposed to any risks beyond those normally associated with CRT systems, transvenous lead systems, or their implant procedure. Because only patients who have existing ICD systems or who meet clinical indications for ICD implant will receive

CRT-D implant, there is no additional risk for these patients aside from the CRT risks described here for all patients in this study. With the exception of the risks associated with the device and implant procedure implant, the risks associated with metabolomics blood draw are considered minimal, Therefore, the risk analysis in this section is specific to the implantation, management and therapy from the implanted CRT system. The subject will remain in the study for intention to treat analysis, but the investigator will avoid any procedures that may be determined harmful.Study subjects will receive a CRT device with the associated three leads (one right atrial, one right ventricular and one left ventricular lead).

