All unresolved adverse events should be followed by the investigator until the events are resolved, the subject is lost to follow-up, or the adverse event is otherwise explained. At the last scheduled visit, the local investigator should instruct each subject to report, to the local investigator, any subsequent event(s) that the subject, or the subject's personal physician, believes might reasonably be related to participation in this study. The local investigator should notify the study regulatory sponsor of any death or adverse event occurring at any time after a subject has discontinued or terminated study participation that may reasonably be related to this study. The sponsor should also be notified if the local investigator should become aware of the development of problems, cancer or of a congenital anomaly in a subsequently conceived offspring of a subject that has participated in this study.

Preexisting Condition

A preexisting condition is one that is present at the start of the study. A preexisting condition should be recorded as an adverse event if the frequency, intensity, or the character of the condition worsens during the study period.

Unanticipated Problems Involving Risk to Subjects or Others (UPIRTSO)

Any unanticipated problem or adverse event that meets all of the following three criteria:

- Serious: Serious problems or events that results in significant harm, (which may be physical, psychological, financial, social, economic, or legal) or increased risk for the subject or others (including individuals who are not research subjects). These include: (1) death; (2) life threatening adverse experience; (3) hospitalization inpatient, new, or prolonged; (4) disability/incapacity persistent or significant; (5) birth defect/anomaly; (6) breach of confidentiality and (7) other problems, events, or new information (i.e. publications, DSMB reports, interim findings, product labeling change) that in the opinion of the local investigator may adversely affect the rights, safety, or welfare of the subjects or others, or substantially compromise the research data, AND

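### The primary safety rate covers randomised participants only, and only successful implants are randomised, so procedural complications in people attempted but never randomised fall outside it; the direction and size of the effect are unknown

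*Combined protocol and SAP*

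**What the plan says.** The safety population is defined the same way in two places. The Study Overview, under Primary Safety Objective, has "Freedom from system-related complications in randomized subjects will be calculated at 1, 6, and 12 months post implant". The Primary safety objectives section has "Freedom from system-related complications in randomized participants will be calculated at 1, 6, and 12 months post-implant to determine the safety profile". Both list six complications, among them pocket hematoma, pneumothorax and myocardial perforation, which can occur during or just after the procedure. The latter section adds: "This safety profile will be balanced against efficacy to quantify the risk-benefit ratio".

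Study design and randomization decides who enters that population: "Participants who have a successful CRT implantation will be randomly assigned 1:1 to have the CRT programmed on" or off, "within 7 days of completing the implant procedure". Success is not defined.

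Recording of events is broader than the safety rate. Safety and Adverse Events covers "All adverse events occurring related to the procedure or protocol required testing during the study", and the instructions on adverse event recording later in the protocol repeat that procedure-related events must be recorded. Under Post-study Adverse Event, "All unresolved adverse events should be followed by the investigator until the events are resolved". Safety and Adverse Events also says "The subject will remain in the study for intention to treat analysis", without saying which subjects are meant. Nothing in the documents brings the recorded events of never-randomised participants into the primary safety rate.

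**The concern.** The safety clock starts at implant, but membership of the safety population is settled afterwards, partly by the outcome of the procedure. A participant whose implant fails, or who does not reach randomisation in the following days, drops out of the calculation together with any listed complication.

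This matters because the rate is the trial's only primary safety measure and is the risk side of the planned risk-benefit comparison. The Study device section says that CRT in this LVEF range is not FDA-approved. Someone considering this use faces the risk of an attempted implant, whereas the planned rate describes the risk among those whose implant succeeded and who were then randomised.

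**Working it through.** **Plan's own figure.** There is none to reproduce. The documents give no complication rate, implant failure rate, safety threshold or safety hypothesis. The only related numbers are 100 enrolled (Study design and randomization) and 50 + 50 = 100 analysed in the power calculation (Sample Size Considerations and Statistical analysis), with no allowance for people attempted but not randomised.

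**Formula.** Let f be the share of attempted participants who are not randomised, q their listed-complication rate and r the rate in the randomised.

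- Planned rate = r
- All-attempted rate = (1 − f) × r + f × q
- Difference (all-attempted minus planned) = f × (q − r)

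The planned rate is too low if q > r, correct if q = r and too high if q < r. With f = 0 the difference is zero.

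**At 1 month. Every input is an assumption.** With f = 5% and r = 5%:

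| q | All-attempted rate | Difference (points) |
|---|---|---|
| 0% | 0.95 × 5% + 0.05 × 0% = 4.75% | −0.25 |
| 5% | 0.95 × 5% + 0.05 × 5% = 5.00% | 0 |
| 20% | 0.95 × 5% + 0.05 × 20% = 5.75% | +0.75 |

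Over f of 3–10%, r of 5–10% and q of 0–50%:

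- minimum: 0.10 × (0 − 0.10) = −1.0 point
- maximum: 0.10 × (0.50 − 0.05) = +4.5 points

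**In counts.** Take 100 randomised with 5 complicated, so the planned rate is 5/100 = 5.0%. Add 5 attempted but not randomised:

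- none complicated: 5/105 = 4.8%
- one: 6/105 = 5.7%
- two: 7/105 = 6.7%
- all five: 10/105 = 9.5%

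If 10 are added instead and all 10 are complicated, the rate is 15/110 = 13.6%, or 8.6 points above the planned rate. The size follows the assumption chosen. For scale, the exact 95% confidence interval for 5/100 is 1.6% to 11.3%.

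**At 12 months.** Assume f = 5%, and in the randomised 5% complicated by 1 month and 8% by 12 months. Suppose the never-randomised have q = 5% and carry no hardware, so they have no later device events.

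- Kept in the denominator: 0.95 × 8% + 0.05 × 5% = 7.85%. This is the actual cumulative proportion among all attempted.
- Censored after 1 month: the late risk in the randomised is 0.03/0.95 = 3.16%, so the estimate is 1 − 0.95 × (1 − 0.0316) = 8.00%.

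Censoring gives people without a device the late risk of device carriers. A later all-attempted figure should therefore keep them in the denominator.

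**The case against.** The strongest reply concerns consequence, not wording. This is a pilot and no pass/fail decision rests on the rate. The documents do not show that any attempted participant will go unrandomised, and the planned numbers imply that none will. In the f = 5%, r = 5% illustration the shift is at most 0.75 points, far inside the sampling uncertainty of 5/100. These points stand and limit the priority. They do not remove the gap, because imprecision does not excuse a population chosen after the procedure, and the randomised-only rate cannot itself show whether the gap matters.

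A second reply is that the events are recorded anyway. That also stands, but recording an event is different from counting it in the rate. The intention-to-treat sentence does not help, since it neither names the subjects it covers nor alters the safety population.

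A third reply is that follow-up of never-randomised participants is not assured. This is fair. The Schedule of Events neither includes nor excludes them, so their 6- and 12-month ascertainment cannot be taken for granted.

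A reader might infer three stronger things that the documents do not support:

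- **That the plan understates risk.** A complication can itself prevent a successful implant, so this is plausible. But uncomplicated failed implants leave the denominator too, and no figure in the documents settles the sign.
- **That all complications before randomisation are lost.** Early events in people later randomised can still count, because the rate runs from implant.
- **That these events go uncollected.** Procedure-related events are to be recorded and unresolved ones followed.

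**Conclusion.** The gap in the analysis population is real and follows from two explicit rules: safety is calculated in the randomised, and only successful implants are randomised. The planned rate is conditional on implant success and is not the risk of an attempted implant.

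The sign and size of the difference are unknown. The range of −1.0 to +4.5 points at 1 month rests wholly on assumed values of f, q and r, and would be wider if q above 50% were allowed. The effect is nil if everyone attempted is randomised or if the two complication rates are equal. This is a cheap improvement of minor to moderate priority. The text supports the gap with high confidence; its practical consequence is not shown.

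**What to change.** In the Study Overview and in Primary safety objectives:

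- **1 month.** Calculate the periprocedural rate in all participants in whom the study implant procedure was started, with time zero at the start of the procedure, using the procedure-related events already recorded.
- **Accounting.** Report the number attempted but not randomised, the reasons, and their listed complications.
- **6 and 12 months.** Keep the randomised-only rate and show beside it the all-attempted cumulative proportion. Count earlier events, and keep participants without hardware in the denominator without censoring them.
- **Risk-benefit statement.** Say that efficacy stays in the randomised set, and name the population behind each side of the comparison.

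The cost is a second rate to report and a 1-month contact that also covers the few never-randomised participants. Later events in any of them with retained hardware may be less completely ascertained, and this should be stated. The safety figure may become less favourable. The efficacy analysis does not change.
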